##### Analysis of GM and beta-D Glucan Assays

Sensitivity, specificity, positive predictive value, and negative predictive value of the GM assay and beta-D glucan assay will be determined using standard formulas and EORTC/MSG criteria as the gold standard. Please see Section 13.8 for additional statistical considerations for this secondary aim.

##### SNP Analysis in Genes Involved in Immunity

We will perform haplotype analysis using previously established methods for unrelated subjects. To deal with possible false positive or negative results, we will perform the following. First, in order to handle the concern of multiple testing, we will adjust the *P* value required for statistical significance by the false discovery rate, which is an approach to multiple testing that is a compromise between unadjusted tests of significance and more traditional, but too conservative Bonferonni adjustment. Second, to handle the potential for population stratification, all analyses will be performed with and without adjustment by ethnicity. We will use Kaplan-Meier analyses to evaluate time to any IFI, and determine

the impact of candidate gene SNPs using the log rank test. For the exploratory analysis on the relationship between IFI and the identified SNPs in the candidate genes, study participants will be grouped based on the genotype of specific SNP(s). If the primary analysis suggests no difference in IFI between caspofungin and fluconazole, standard log rank analysis will be used to compare the time to IFI between patient groups defined by the SNP(s); stratified log rank test adjusting for treatment arm will be considered if the data suggest a treatment difference on IFI between caspofungin and fluconazole.

In developing a clinical prediction model for IFI, the outcome is time to IFI and the predictors can be demographic factors, clinical factors, co-morbid conditions, and SNPs. Standard survival analysis such as Cox model (or competing risk analyses modeling the cause-specific hazard or cumulative incidence function, if needed) will be used to build predictive models. Unlike an explanatory model, inclusion of variables into the predictive model will depend only on its ability to improve the prediction of the outcome and does not necessarily have to be based on biologic plausibility (although plausibility could make a prediction rule more accessible to clinicians). On the other hand, a clinically useful predictive model also needs to be practical in that the variables must be available in most clinical settings. We will take into account these factors in developing the predictive models, and internal cross-validation techniques will be considered in assessing the models.

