### 9.3.3 Sample size with power justification

A total of approximately 550 eligible patients will be randomized to the 2 arms (at least 275 patients on each arm). Patients will be followed for infection outcome data until criteria in Section 8.3 has been met unless the patient is off study per Section 8.2 prior to meeting criteria in 8.3.

Since the current AAML1031 proposal plans 4 courses of chemotherapy with about 1 month duration for each course, it implies that likely many study participants will be followed for IFI for about 5 months. The power calculation assumes an IFI incidence in the fluconazole group of 8% and an IFI incidence in the caspofungin treatment groups of 2% at 5 months. The hazard ratio is 0.24. We assume up to 10% of patients may have early termination of follow up on IFI due to change in AML therapy such as refractory disease, relapse, or death. It is estimated that up to 25% of patients treated on or per AAML1031 may go to SCT prior to finishing all 4 courses. Therefore, altogether up to 35% patients may not be followed until the end of 5 months for IFI. With at least 275 patients on each arm, a planned 5-month follow up on each patient and up to 35% patients being censored by 5 months, we have about 80% power to detect the expected difference in time-to-IFI curves between the 2 arms (8% vs. 2% at 5 months) in a log rank test with 2-sided alpha level of 0.05. In the calculation, both failure and censoring are assumed to follow an exponential distribution during the 5 months. The majority of the censoring events prior to 5 months are expected to be due to SCT which likely occur later in the 5 months, so the exponential censoring distribution might not be a very good approximation but should be conservative in power consideration.

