### 13.8 Statistical Design

#### 13.8.1 Sample Size and Estimated Event Rates

The parent trial comparing prophylaxis with caspofungin to fluconazole in newly diagnosed AML patients anticipates enrollment of at least 275 patients for each arm with a total cohort of approximately 550 patients. As noted above we anticipate that at least 80% of the patients enrolled in the parent trial will also be enrolled in this ancillary study. This will result in 220 patients from each study arm. Consent for testing will be included as a part of the parent trial enrollment, thus significantly limiting the need for additional resources to complete this biomarker study.

The estimated number of probable or proven IFI events for final analyses will be different for both proposed biomarkers as they account for different types of fungal infections and the incidence for each will vary by study arm. The Fungitell Assay has the potential to identify most pathogenic fungi and thus a majority of the probable or proven IFIs will be considered as true events (excluding IFIs from *Zygomycetes* and *Cryptococci*). The Platelia *Aspergillus* EIA is specific for *Aspergillus* and thus only probable or proven IA will be considered as true events for that analysis.

Based on Section 9.3.3 of the parent trial the estimated incidence of IFI for patients in the fluconazole group is 8% and 2% in the caspofungin arm. Assuming the enrollment of 220 patients in each study arm, there would 18 IFI events in the fluconazole group and 4 IFI events in the caspofungin group. Based on data from the CCG 2961 AML trial, one-third of microbiologically proven fungal infection were the result of *Aspergillus*. Therefore, it is estimated that 6 of the 18 IFI events in the fluconazole group will be IA and between 1 and 2 of the IFI events in the caspofungin group will be IA.

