## 14.0 SPECIAL STUDIES SPECIMEN REQUIREMENTS

### 14.1 Single Nucleotide Polymorphisms (This study is optional)

Genotypes of interest in genes mediating immune function will be determined by review of experimental data from AAML0531 and review of the literature. Genotyping will be conducted as part of 1R01 CA133881 and analysis will be performed on the Taqman Open Array Platform according to the manufacturer's instructions.

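### With about 22 IFI events expected, log-rank p-values for SNPs with small genotype groups are too small in the far tail that the false discovery rate uses

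*Combined protocol and SAP*

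**What the plan says.** The SNP part of section 9.3.4 uses Kaplan-Meier analysis of time to IFI and assesses "the impact of candidate gene SNPs using the log rank test". Participants are grouped by the genotype of particular SNPs, and haplotype analysis is also planned. If the arms differ on IFI, a "stratified log rank test adjusting for treatment arm will be considered". For multiple testing, the plan adjusts the P value "required for statistical significance by the false discovery rate". All analyses are to be run with and without adjustment for ethnicity.

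The section does not state the genotype coding (three groups, dominant or recessive), a minimum group or event count, the number of SNPs, the FDR level, or any exact or permutation reference distribution. Section 14.1 leaves the SNP list open: "Genotypes of interest in genes mediating immune function will be determined by review of experimental data from AAML0531 and review of the literature". It also makes the sub-study optional. No other section deals with sparse genotype groups.

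**The concern.** The log-rank p-value normally comes from a chi-square approximation, which needs a reasonable number of expected events in each group. Here the total is about 22, so a rare genotype group may expect well under one. In such a group a single chance cluster of two events produces a very small p-value.

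An FDR procedure acts on the smallest p-values, where the approximation is worst, and it cannot correct inputs that are wrong. Section 9.3.4 adopts the FDR to deal with false positive and false negative results. If the inputs fail, objective 1.2.5 could report a SNP association that is an artefact of the approximation, and that SNP could then enter the prediction model of objective 1.2.6.

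**Working it through.** **1. Event count.** Section 13.8.1 gives "18 IFI events in the fluconazole group and 4 IFI events in the caspofungin group" for 220 patients per arm. This reproduces: 220 × 0.08 = 17.6 and 220 × 0.02 = 4.4, which round to 18 and 4, total 22. That count is for the biomarker cohort and applies no early censoring.

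For the full trial, section 9.3.3 assumes 275 per arm, 8% and 2% IFI at 5 months, up to 35% censored by 5 months, and exponential times.
- Monthly hazards: −ln(0.92)/5 = 0.01668; −ln(0.98)/5 = 0.00404; censoring −ln(0.65)/5 = 0.08616. The ratio 0.00404/0.01668 = 0.242 agrees with the stated 0.24.
- Expected events = n × λ/(λ+γ) × [1 − exp(−5(λ+γ))].
- Fluconazole: 275 × 0.1622 × (1 − 0.92 × 0.65) = 17.9.
- Caspofungin: 275 × 0.0448 × (1 − 0.98 × 0.65) = 4.5.
- Total 22.4.

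The range is about 18 (440 patients with this censoring) to 27.5 (550 with none). SNP participation is optional and no number is stated, so the count may be lower than 22.

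**2. Hand check.** Assume allele frequency 0.10. Expected minor homozygotes are 550 × 0.01 = 5.5, with 22.4 × 0.01 = 0.22 expected events. Suppose 2 of 22 events fall among them. With k homozygotes, E = 22k/550, V = 22(k/550)(1 − k/550) and z = (2 − E)/√V. The exact figure is the hypergeometric chance of 2 or more events.

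| k | E | V | z | Chi-square p | Exact p |
|---|---|---|---|---|---|
| 5 | 0.20 | 0.198 | 4.04 | 0.00005 | 0.014 |
| 6 | 0.24 | 0.237 | 3.61 | 0.0003 | 0.021 |

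**3. Null rejection rate by group size.** Two-group log-rank test simulated with no SNP effect, N = 550, the section 9.3.3 event and censoring model, 40,000 trials per row.

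| Share in smaller group | Expected events in it | Rate at 0.05 | Rate at 0.001 |
|---|---|---|---|
| 1% | 0.2 | 0.055 | 0.018 |
| 2% | 0.4 | 0.061 | 0.010 |
| 4% | 0.9 | 0.047 | 0.0063 |
| 6.25% | 1.4 | 0.045 | 0.0043 |
| 9% | 2.0 | 0.039 | 0.0030 |
| 16% | 3.6 | 0.046 | 0.0019 |
| 25% | 5.6 | 0.050 | 0.0010 |
| 50% | 11.2 | 0.049 | 0.0007 |

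At 0.05 the test is close to nominal throughout. At 0.001 the excess is 10- to 18-fold for groups of 1–2%, about 3-fold at 9%, and absent from about 25%. Stratifying by arm leaves this pattern essentially unchanged.

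**4. Three genotype groups (2 df), same model.** At nominal 0.001 the null rate is 1.5–1.6% across independent runs for allele frequency 0.10, then 0.47% at 0.2, 0.28% at 0.3 and 0.10% at 0.5.

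**5. Effect on the FDR.** Benjamini-Hochberg at q = 0.05 with no real SNP effect; chance of at least one false discovery:
- Three groups, allele frequency uniform on 0.05–0.5: about 16%, 25% and 38% with 20, 50 and 100 SNPs.
- Three groups, allele frequency at least 0.2: about 7–12%.
- Dominant coding: about 4–7%.

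**The case against.** The strongest reply is that small genotype groups are an assumption. The documents give no SNPs, allele frequencies, coding, SNP count or FDR level, and section 9.3.4 does not say that the log-rank p-value must be asymptotic. Under dominant coding the problem nearly disappears. Pooling sparse groups below 2 expected events brought the three-group procedure to 5.5–7% by itself. The genotype-group comparison is called exploratory and the sub-study is optional.

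Most of this stands as a limit on the point. A reader might infer that all the SNP p-values are far too small, or that the trial would report false SNPs as a matter of course. The documents do not support either reading: the distortion depends on group size, and with 20 SNPs under the unfavourable coding about 84% of null trials would report none.

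It does not remove the point. The chi-square version is the usual default, the plan allows three-group and haplotype comparisons, and nothing in it screens out rare groups. Good behaviour at 0.05 does not help, because the FDR works in the tail. The exploratory label does not settle the matter either, since objective 1.2.5 is a listed secondary objective to test association.

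**Conclusion.** The concern holds conditionally. With about 22 events, chi-square log-rank p-values are anti-conservative in the far tail when a genotype or haplotype group holds under roughly 10% of patients, or about 2 or fewer expected events. In the unpooled three-genotype case this raises the false-discovery chance under the global null from 5% to about 16–38% for 20–100 SNPs. These figures assume allele frequency uniform on 0.05–0.5, independent SNPs, q = 0.05 and all 550 patients genotyped; none of these is in the documents. With common alleles only, the rise is modest. With dominant coding, or groups of about 25% or more, there is essentially none.

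A reader might also infer that the caspofungin–fluconazole comparison is affected. It is not: the arms are equal in size, and the effect is confined to objective 1.2.5 and the SNP inputs to 1.2.6.

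**What to change.** Add to the SNP analysis in section 9.3.4:

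- Each SNP or haplotype p-value entering the FDR is a permutation p-value from the same log-rank statistic, with genotype permuted within randomized arm and within the de novo/other stratum. For the ethnicity-adjusted analysis, permute within ethnicity as well; otherwise the reference distribution does not match that analysis.
- Minor homozygotes are pooled with heterozygotes when the rare group's expected event count is below a stated minimum, for example 2.
- The genotype coding, number of SNPs and FDR level are stated before the genotype data are analysed, and the number of permutations is large enough to resolve p-values at q divided by the number of SNPs (for example 0.05/100 = 0.0005).

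The cost is a few sentences, computing time and fewer SNPs declared significant. Enrolment, sampling and the primary analysis do not change.

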#### 9.3.5 Interim Monitoring

Study data will be reviewed by DSMC twice a year during the first 2 years of study activation, and once a year thereafter upon their approval if the study goes smoothly. We plan two formal interim efficacy analyses comparing treatment outcomes between the 2 arms, after approximately one third and two thirds of the patients have completed study treatment and IFI observation. The endpoints for the interim analyses include time to the following individual event: IFI, invasive aspergillosis, death. Log rank test will be the primary method for these interim analyses; monitoring boundary for the primary endpoint on IFI will be based on Lan-Demet's method with spending function at . Competing risk analyses such as estimating the cumulative incidence of the event and Gray's test for IFI or IA will be performed as well to check that corresponding competing risk analyses do not suggest a different conclusion than the standard survival analyses.

Informal interim safety analyses will also be performed at each DSMC review on the observed adverse events between the 2 arms. This analysis will include all patients who receive at least one dose of study medication. The proportion of patients experiencing any grade 4 or higher non-hematological adverse event will be compared between the 2 groups using chi-square tests. For this monitoring, each test will be at two-sided level of 0.05 without adjustment for multiple testing, to ensure us being alerted by any potential difference in adverse events between the 2 arms. If a significant difference between the 2 arms is found ( $p < 0.05$ ), the study committee will examine the adverse event profiles for safety considerations and decide if any action needs to be taken.

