## 7.2 Optional Studies

### 7.2.1 Galactomannan and (1→3) Beta-D Glucan Assays

Two antifungal antigen assays (Platelia *Aspergillus* EIA and Fungitell Assay) will be performed during the period of neutropenia in order to identify IA only and all IFI respectively. 6 mL of peripheral blood will be collected in a gold top serum-separator tube (provided by MiraVista) twice weekly. See Section 13 for sample collection, processing and shipping details. For each period of neutropenia, documentation of exposure or lack of exposure to each of the following will be performed: amoxicillin-clavulanate, piperacillin-tazobactam, and intravenous immunoglobulin. Documentation of infection with *Pneumocystis jiroveci*, *Penicillium* spp., *Histoplasma capsulatum*, *Geotrichum* spp., or *Neosartoria* spp. will occur through microbiology or pathology reporting and through routine adverse event reporting. See Section 11 for sample collection and shipping details.

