**11.4 Routine Adverse Event Reporting**

**Note:** The guidelines below are for routine reporting of study specific adverse events on the COG case report forms and do not affect the requirements for **CTEP-AERS** reporting.

The NCI defines both routine and expedited AE reporting. Routine reporting is accomplished via the Adverse Event (AE) Case Report Form (CRF) within the study database. For this study, routine reporting will include all toxicities reported via CTEP-AERS and all Grade 4 and higher non-hematological Adverse Events.

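### The one adverse-event comparison with a threshold pools all Grade 4+ non-hematological events including IFI, so it is a weak detector of drug toxicity, and the plan states no DSMC role in acting on its result

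*Combined protocol and SAP*

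**What the plan says.** Section 9.3.5 of the combined protocol and SAP provides for safety monitoring as follows.

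- Timing: "Informal interim safety analyses will also be performed at each DSMC review on the observed adverse events between the 2 arms". The DSMC meets twice a year for two years, then yearly if it agrees.
- Population: "This analysis will include all patients who receive at least one dose of study medication".
- Variable and test: "The proportion of patients experiencing any grade 4 or higher non-hematological adverse event will be compared between the 2 groups using chi-square tests".
- Threshold: "each test will be at two-sided level of 0.05 without adjustment for multiple testing", chosen openly so that a possible difference is not missed.
- Response to p < 0.05: "the study committee will examine the adverse event profiles for safety considerations and decide if any action needs to be taken".

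Section 11.4 says what reaches the adverse-event form: events reported through the expedited system, and "all Grade 4 and higher non-hematological Adverse Events". Infections are not excluded there or in 9.3.5. Section 9.3.3 plans on an "IFI incidence in the fluconazole group of 8" percent and a caspofungin incidence of 2 percent at 5 months.

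Safety is not among the objectives in Section 1, and Section 9.3.4 names no adverse-event comparison. Death is compared between arms at the two formal interim analyses, but the monitoring boundary in 9.3.5 is stated for IFI only.

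**The concern.** The comparison is meant to alert the trial to any difference in harm. Two features work against that.

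First, the variable is one yes/no per patient for any severe non-hematological event in a population receiving intensive AML chemotherapy. Severe events from chemotherapy will occur in both arms and dilute an excess confined to one organ system. The risks that Sections 6.1 and 6.2 list (such as hepatic failure, anaphylaxis, QT prolongation or arrhythmia, and Stevens-Johnson syndrome) are of that confined kind.

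Second, IFI is inside the variable. If caspofungin works as planned, fewer Grade 4+ IFIs on that arm offset part of any toxicity excess. With no toxicity difference, the same effect can produce a safety alert that is really an efficacy signal.

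The decision after an alert adds to this. By-arm event profiles, partly reflecting the primary endpoint, would go to the committee running an open-label trial in which the work-up for IFI is at the local physician's discretion (Section 10.2).

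**Working it through.** **The plan's own figures.** The documents give no power or error rate for the safety test. The figure carried into this check is the IFI assumption in 9.3.3, which is coherent. ln(0.98)/ln(0.92) = 0.242, against a stated hazard ratio of 0.24. With 275 per arm and 35% exponential censoring, the expected events are 17.9 + 4.5 = 22.4, and the Freedman formula gives about 82% power, against a stated 80%.

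**Inputs.** From the documents: 275 per arm (taken as all dosed), IFI 8% versus 2%, two-sided 0.05 chi-square. Assumed: background Grade 4+ rate b of 20-50%, share f of IFIs reaching Grade 4+ of 0 to 1, and drug toxicity of 1% on fluconazole and 6% on caspofungin.

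**Step 1: how much IFI can mask.** If no patient with a Grade 4+ IFI has another Grade 4+ event, IFI hides f × (8 − 2) points: 6 if all IFIs are Grade 4+, 3 if half, 1.5 if a quarter. If IFI and other events overlap independently and f = 1, the hidden excess is (1 − b)(1 − 0.92/0.98):

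- b = 10%: 5.5 points
- b = 30%: 4.3 points
- b = 50%: 3.1 points
- b = 70%: 1.8 points

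**Step 2: chance that the pooled test flags caspofungin.** Per arm, P(any event) = 1 − (1 − b)(1 − f × IFI)(1 − toxicity). For b = 30% and f = 0.5:

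- fluconazole: 1 − 0.70 × 0.96 × 0.99 = 33.5%
- caspofungin: 1 − 0.70 × 0.99 × 0.94 = 34.9%

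A 5-point toxicity excess becomes 1.4 points. The probabilities below are for an uncorrected chi-square test significant in the direction of caspofungin harm.

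| Share of IFIs Grade 4+ | b = 20% | b = 30% | b = 50% |
|---|---|---|---|
| None | 20.8% v 24.8%: flagged 20% | 30.7% v 34.2%: 14% | 50.5% v 53.0%: 9% |
| Half | 24.0% v 25.6%: 6.3% | 33.5% v 34.9%: 5.3% | 52.5% v 53.5%: 4.5% |
| All | 27.1% v 26.3%: 1.5% | 36.2% v 35.5%: 1.6% | 54.5% v 53.9%: 2.0% |

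Tested alone, 1% versus 6% is flagged 93% of the time. The fall from 93% to 9-20% is dilution by background events. The further fall to about 1.5-6% is due to IFI.

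**Step 3: a second parameterisation.** Take a true +6 points on a 30% background, no overlap, 275 per arm, and count a significant result in either direction. The alert chance is 32% with no IFI counted, 20% at f = 0.25, 11% at f = 0.5 and 5% at f = 1. With no IFI counted it is 23% at 183 per arm and 14% at 92 per arm. The test is weak even without IFI, and more so at early reviews.

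**Step 4: firing on efficacy.** With no toxicity difference and b = 20-50%, fluconazole is flagged in 11-26% of trials if all IFIs are Grade 4+, 6-10% if half, and 4-5% if a quarter. Chance alone gives about 2.5% in that direction.

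**Step 5: chance alerts.** Assume six reviews at 25, 50, 87, 125, 200 and 275 per arm and equal event rates of 20-50%. The chance of at least one p < 0.05 is about 18-19%. The plan accepts this on purpose. It matters here only because each alert opens by-arm profiles to the study committee.

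**The case against.** A fair opponent would make these points.

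- **Most of the loss is not IFI.** Correct. Step 2 shows that background dilution accounts for most of it. A reader might infer that the IFI benefit cancels a real toxicity excess. At most it offsets 6 points, and only if every IFI is Grade 4+ and none occurs in a patient already counted. Partial masking is what the figures support.
- **The inputs are favourable to the concern.** Partly so. The 6% has no source. Section 2.2.2.2 reports 3 of 171 children (1.8%) stopping caspofungin for drug-related events, and Section 6 lists the gravest risks as rare (under 5 in 100). The 93% also needs the whole excess to fall in one category. Smaller or scattered excesses would be harder to see by any method.
- **The DSMC is not bypassed.** Correct. A reader might infer that the alert goes to the study committee instead of the DSMC. The analysis is run at each DSMC review, nothing limits what the DSMC sees, and its charter is not among the documents. What is missing is a stated DSMC role once p < 0.05.
- **All-cause counting is a legitimate net-harm measure that avoids attribution.** This stands, and is why the pooled test should stay. It also argues against removing all infections: Section 6.2 lists pneumonia, sepsis and bacteremia as caspofungin toxicities.
- **Infections may not reach the form.** Section 7.2.1 says documentation of certain infections "will occur through microbiology or pathology reporting and through routine adverse event reporting", but that covers five named organisms relevant to the optional assay study. The point rests on Section 11.4, which takes all Grade 4+ non-hematological events.
- **The screen is labelled informal.** It is, but it is the only adverse-event rule with a threshold, and examination of profiles is prescribed only as the response to that threshold.

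A reader might also infer that events after transplant conditioning or relapse therapy enter the comparison. Sections 9.3.5 and 11.4 give no onset window, but Section 12.0 places the case report forms and submission schedule outside these documents, so this is not shown.

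**Conclusion.** The point holds in limited form. The single thresholded adverse-event comparison is insensitive to organ-specific toxicity, mainly because background events dilute it and secondarily because the efficacy endpoint is counted in it and runs the other way. Under the stated assumptions it flags a 6% versus 1% excess in about 9-20% of trials without IFI and about 1.5-6% with half to all IFIs at Grade 4+. It can also fire on efficacy alone.

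The direction follows from the text. The size depends on three quantities the documents do not give: the background rate, the Grade 4+ share of IFI and the toxicity excess. On governance, the gap is an unstated DSMC role after an alert in an open-label trial. No change to sample size or to the primary analysis follows. This should be changed, because the remedy is cheap and replaces a rule that does not serve its stated purpose.

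**What to change.** Amend Section 9.3.5 in three places.

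1. Keep the pooled test and add the same comparison with IFI events removed. Remove IFI only, not all infections, and remove the event rather than the patient, so that someone with an IFI and another Grade 4+ event still counts.
2. At every DSMC review, whatever the p-value, show by-arm counts of Grade 4+ events by category: hepatic, allergic or infusion-related, cardiac, skin, and non-fungal infection.
3. State that the DSMC examines the by-arm profiles and makes the recommendation, and that the study committee receives the recommendation.

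Item 2 matters most. Under the assumptions above, item 1 alone brings detection back only to about 9-20%. Item 2 supplies counts for judgement rather than a test, so the 93% should not be read as the performance of the amended plan.

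The cost is a wording change and a few tables from events already collected under Section 11.4. The downside is some additional chance signals for the DSMC to weigh.
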